## Discussion

The main objective of this project will be to examine the feasibility of a novel Facebook 387 intervention to address patient adherence to cardiac rehabilitation. Improving uptake and 388 adherence to cardiac rehabilitation is of paramount importance in the secondary prevention of 389 CHD. This study will use the validated BREQ-3 questionnaire, the PNSE scale, and examine the 390 effect of a Facebook intervention on number of cardiac rehabilitation sessions attended. 391 Applying the self-determination theory, the research team will provide educational and provider 392 support postings on a private Facebook group. The participants will have the opportunity to 393 learn and interact with other participants in this social media platform. The current study has the 394 potential to affect a change in patient motivation for exercise and cardiac rehabilitation 395

adherence, thus reducing complications and hospital readmissions among patients eligible forcardiac rehabilitation.

### 398 Limitations and Unanticipated Problems

Limitations for this study include the variable number of sessions paid for by non-399 Medicare and non-Medicaid insurances. This could potentially affect motivation or participation 400 401 in the Facebook group and cardiac rehabilitation itself if the patient has few sessions that are covered by insurance. Feasibility concerns for the pilot include obtaining a large enough cohort 402 of patients in order to have peer support, especially for those who enroll in the early stages of the 403 study. Data will not be included for the first 8 participants, in order to ensure that there is a large 404 enough group of Facebook users to enable social networking among participants. Additionally, 405 patient "hits" on the Facebook group rely on self-report and are therefore subject to reporting 406 bias. 407

408 There are limitations to this feasibility study that can be addressed in a larger trial. 409 Patients who are not current Facebook users were excluded from the pilot trial. If Facebook is 410 demonstrated to be a feasible venue for presenting and testing motivation for exercise, those who are not currently on Facebook should be included in a larger trial. The fact that patients may see 411 412 each other in cardiac rehabilitation presents a potential for diffusion bias, demoralization or rivalry. This has been minimized to the extent that few participants are likely to communicate 413 about the study in cardiac rehabilitation sessions due to the number of classes and facilities; 414 however it will need to be a consideration for this and larger studies. 415

416

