# 144 Study Objectives

The purpose of the current randomized pilot trial is to determine the feasibility of using a Facebook intervention, providing education, peer support and provider support, to affect change in motivation and self-determination for exercise, and adherence to cardiac rehabilitation in patients with CHD during a 12-week Phase II cardiac rehabilitation program. It is hypothesized that:

150	1.	Scores for motivation for exercise overall will increase for patients exposed to a
151		Facebook intervention and across individual motivational subtypes (regulations)
152		relative to a comparison group who receive educational handouts and emails.
153	2.	Percentage of cardiac rehabilitation sessions attended will be higher relative to a
154		comparison group who receive educational handouts and emails.
155	3.	Engagement in the private Facebook group (number of "hits" and "likes") will predict
156		number of cardiac rehabilitation sessions attended and the change in motivation. The
157		feasibility of a larger trial will be based on sample size and participants' engagement
158		in the Facebook group.
159		
160		
161		

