#### 168 Setting and Sample

The setting for this study will be in the outpatient cardiac rehabilitation at the main 169 170 campus of a large tertiary care center in Northeast Ohio and several satellite facilities in the region, and in patients' homes or other locations where home computers might be accessed. This 171 cardiac rehabilitation program provides ECG-monitored, supervised exercise, dietary guidance, 172 smoking cessation, behavioral counseling and stress reduction. All patients receive an 173 individualized exercise prescription based on functional capacity at intake. Most patients, 174 depending on insurance coverage, will be able to attend up to 3 sessions per week for a total of 175 36 sessions. In addition, patients are given guidance for unsupervised exercise at home. 176

177 All patients who are current and regular Facebook users, have qualified for cardiac 178 rehabilitation (diagnosed with CHD), and are entering cardiac rehabilitation at the main campus 179 of this tertiary care center, will qualify to participate in the study prior to beginning Phase II cardiac rehabilitation. Current Facebook users were chosen as it is important that participants 180 181 are skilled at using the internet and familiar with social media. Regular use will be defined as logging onto Facebook at least 2 times in the last month. Inclusion criteria will include both men 182 and women 18 years of age or older who speak English and live within 100 miles of the main 183 campus of this tertiary care center. Participants must be able to read and understand English in 184

order to read the information sheet and complete the Psychological Need Satisfaction in Exercise
Scale (PNSE) [37] and the Behavioral Regulation in Exercise Questionnaire-3 (BREQ-3). There
will be no exclusion based on secondary diagnosis; however, participants must be able to
exercise well enough to qualify to take part in cardiac rehabilitation.

189 Measures

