### 235 Data Collection Procedures

Volunteers will be recruited from the main campus of this tertiary care center during their 236 inpatient stay or the intake visit for cardiac rehabilitation at the main campus and satellite 237 238 facilities in the region. They may also be approached via phone call if they are on the phase II cardiac rehabilitation schedule due to receiving a referral to the program. Volunteers will be 239 screened for Facebook use and interest in the study, the protocol will be explained, and 240 volunteers will then be sent an email link to an information sheet and 2 questionnaires. The 241 information sheet will address the fact that Facebook is a public forum and names and comments 242 are seen by other participants and the research team. The Facebook group will be private in the 243 sense that those not in the group will not be able to see the content. Participants will receive a 244 baseline BREQ-3 questionnaire and PNSE scale in the email link that will follow the information 245 246 sheet. Participants will then be randomized to Facebook versus comparison groups using blocked randomization (Figure 2). 247

248

249

250

Intervention. The Facebook intervention will include peer support, education, provider support and text message prompts when new posts are added. These interventions are designed to minimize pressure, offer choices, and allow for peer interaction, positive feedback, guidance and direction, in order to provide support for competence, autonomy and relatedness. Competence will primarily be supported with use of educational posts in the Facebook group. Autonomy support will come from the provider posts. Finally, relatedness will be supported by peer interaction and engagement in the Facebook group.

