# 336 Data Analysis

337	Statistical Methods. This is a feasibility study and the sample size obtained will determine if
338	the study is appropriately powered to detect the desired effect size. Patient characteristics will be
339	summarized by group using frequencies and percentages for categorical factors, and means and
340	standard deviations for continuous measures. In order to examine the primary outcome,
341	differences in change in motivation between groups, overall motivation using the RAI from the
342	BREQ-3 will be evaluated using analysis of covariance (ANCOVA) models. Mean differences
343	with 95% confidence intervals for group differences will be presented. Multivariate analysis of
344	variance models will be used to evaluate differences in the change across individual motivation
345	subtypes (regulations), using the BREQ-3, between groups overall. If significant, separate
346	ANCOVA models for each subtype will be fit. Similar ANCOVA models will be used to
347	compare changes in needs satisfaction scores, overall and separately among the three subscales,
348	between groups. Two-sample t-tests will be used to compare number of sessions completed. As
349	a secondary analysis, the relationships between patient characteristics, "hits" and "likes", and the
350	outcome variables RAI change, number of sessions, and needs satisfaction change will be
351	examined using t-tests and Pearson correlations. The correlation between changes in RAI and

352	needs satisfaction will also be evaluated. Analyses will be performed using SAS software
353	(version 9.4; Cary, NC). An overall significance level of 0.05 will be assumed for all tests.
354	Sample Size. The investigators plan to enroll 30 patients in each group. In the first 9 months of
355	2016, cardiac rehabilitation at the main campus of this tertiary care center had approximately 170
356	patient intakes. It is assumed that there will be a similar number of patient intakes for a 9 month
357	period in 2017. Based on Facebook participation rates for those over age 50 [21] and the high
358	participation rates in previous research projects in this facility's cardiac rehabilitation, it is
359	estimated that 40% may meet eligibility requirements and agree to participate. Allowing for use
360	of the first 8 participants to establish the Facebook group, the estimated sample size would then
361	be 60 total participants for randomization to study group who can then be included in

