362	analysis. With this sample size, there will be 86% power to detect large effect sizes (d=0.8) for
363	our study outcomes [40]. The primary aim of this sample size determination is to evaluate
364	whether the proposed intervention is feasible, and to estimate the differences that might exist so
365	that a larger trial that would have adequate power to detect smaller differences could be designed
366	based on what was learned in this pilot study. The sample size of 30 per group was chosen
367	primarily to facilitate a large intervention group, since the value of the intervention is predicated
368	upon interaction among the participants.

369 Human Subjects Protection

This feasibility study has been approved by the Institutional Review Board of this tertiary
care center (Study #16-1456) and is registered at ClinicalTrials.gov, identifier number
NCT02971813.

Participants will be assured that participation in the study at all times is voluntary and will not affect their care in any way. Protection of human subjects for this study will be further ensured through the use of an information sheet. Participants and those in the comparison group will be informed that privacy of medical information will be ensured. However, due to the nature of social media, information or comments posted by the patients in the Facebook group will be visible to others in the group as well as the study team. For this reason, the information sheet will address the fact that comments may be seen by others.

All responses from participants on the Facebook group will be assigned a number and all other identifying information will be removed for data analysis. Any data on paper will be kept in the PI's locked office in a locked filing cabinet. All electronic data will be stored on the PI's computer which requires password entry and in a folder accessible only to the PI and the research team, and on an encrypted thumb drive. Dissemination of findings will be de-identified and reported numerically, in narrative form or in aggregate, with no personal identifiers.

386

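### The session comparison ignores insurance cover, which caps the count and is needed anyway as the attendance denominator; adjusting for it would recover lost precision

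*Combined protocol and SAP*

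**What the plan says.** Under Setting and Sample, most patients, "depending on insurance coverage, will be able to attend up to 3 sessions per week for a total of" 36 sessions. The objective concerns "patients with CHD during a 12-week Phase II cardiac rehabilitation program" (Study Objectives), and 3 sessions a week for 12 weeks gives those 36. The Limitations section says the number of paid sessions varies for insurance other than Medicare and Medicaid. It adds that this could affect motivation or participation "in the Facebook group and cardiac rehabilitation itself if the patient has few sessions that are" covered.

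Four other places bear on the point:

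- **Measures, attendance.** The outcome is sessions attended in 3 months divided by sessions allowed by insurance, times 100. Hypothesis 2 is also worded as a percentage.
- **Data Analysis, Statistical Methods.** The planned test is a two-sample t-test on the number of sessions. No covariate for cover is named there or for the ANCOVA of the relative autonomy index (RAI).
- **Measures, patient characteristics.** Demographic, engagement and clinical variables are listed. Neither insurance nor covered sessions is among them.
- **Data Collection Procedures.** "Participants will then be randomized to Facebook versus comparison groups using blocked randomization". The text names no stratification factor; Figure 2, cited there, is not available to this review.

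**The concern.** The plan identifies a patient-level quantity that limits how many sessions can be attended, and its own outcome definition requires that quantity to be obtained. The analysis then leaves it out. A patient covered for 12 sessions is limited to 12 however motivated; one covered for 36 is not. Differences in cover therefore enter the session count as noise, and with 30 per arm the short-cover patients can by chance fall unevenly. As the characteristics are listed, the baseline table would not show this.

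At stake is how precisely the attendance effect is estimated. The Sample Size section says the pilot is meant to estimate differences from which a larger trial can be designed, so an inflated standard deviation would carry into that design.

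**Working it through.** **The plan's own figure.** "The investigators plan to enroll 30 patients in each group", and "With this sample size, there will be 86% power to detect large effect sizes (d=0.8) for" the study outcomes. The level is 0.05; two-sided is assumed. With a noncentral t on 58 degrees of freedom and noncentrality 0.8 × √(30/2) = 3.10, power is 86.1%. The stated 86% reproduces.

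**Assumptions (not in the documents).** A share f of patients is capped at 12 sessions and attends a mean of 9 (SD 3). The rest attend a mean of 24 (SD 10). The difference in means is 15 sessions. The share f is varied from 10% to 30%.

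**Variance of the count.** Within cover groups: W = (1 − f) × 10² + f × 3². Between them: B = f(1 − f) × 15².

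**Standard error of the arm difference.** Unadjusted: √(2(W + B)/30). Adjusted for cover: about √(2W/30).

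**Chance imbalance.** Its SD, in sessions, is 15 × √(2f(1 − f)/30).

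| f | W | B | B/(W + B) | SE unadjusted | SE adjusted | Imbalance SD |
|---|---|---|---|---|---|---|
| 10% | 90.9 | 20.25 | 18.2% | 2.72 | 2.46 | 1.16 |
| 20% | 81.8 | 36.0 | 30.6% | 2.80 | 2.34 | 1.55 |
| 30% | 72.7 | 47.25 | 39.4% | 2.83 | 2.20 | 1.77 |

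The columns are consistent: at 20%, 2.34² + 1.55² ≈ 2.80². The imbalance is therefore already inside the unadjusted standard error and must not be counted a second time.

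**How often arms differ.** With 12 short-cover patients among 60 split 30/30, the hypergeometric chance that the arms differ by 4 or more is 0.33. Such a difference moves the mean by 4/30 × 15 = 2.0 sessions, or 2.0/2.80 = 0.7 of a standard error.

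**In terms of power.** Take an effect of 0.8 within-cover SDs. The unadjusted test sees d = 0.8 × √(W/(W + B)) = 0.72, 0.67 and 0.62, so power is 79%, 72% and 66%. With adjustment (57 degrees of freedom) it stays at about 86%. This does not contradict the plan's 86%, which holds for d = 0.8 on whatever SD is used.

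**The same patients on the percentage scale.** Capped: 9/12 = 75% (SD 3/12 = 25 points). Others: 24/36 = 66.7% (SD 10/36 = 27.8 points). At f = 20%, the between part is 0.16 × 8.33² = 11.1 and the within part is 0.8 × 27.8² + 0.2 × 25² ≈ 742. Cover then explains 11.1/753 = 1.5% of the variance, and the imbalance SD is 8.33 × √(2 × 0.16/30) = 0.9 points.

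**The case against.** The strongest reply is that the plan already deals with cover: the attendance outcome is a percentage of allowed sessions, and on that scale the problem almost disappears (1.5% of variance against 31%). That is right about the definition. It does not help the planned test, which both the Abstract and the Statistical Methods apply to the count. It does show that analysing the percentage as defined is a complete alternative remedy.

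A second reply is that chance imbalance is not bias, that the t-test keeps its type I error over repeated randomisations, and that a 4-patient imbalance shifts the result by less than one standard error. All of this stands, and the point is confined to precision.

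A third reply is that this is a pilot that discloses the limitation, and that broad entry suits a trial worried about recruitment. This stands against changing who is admitted or how they are randomised. It does not stand against adding one model term.

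A reader might infer more: that admitting short-cover patients is an entry flaw, that patients may have very few or no covered sessions (leaving the percentage undefined), or that randomisation must be stratified by cover. The documents do not support these readings. They say most patients can attend up to 36 sessions, limit the variability to certain insurances, and require patients to have qualified for rehabilitation and be entering it. Very short or zero cover is only hypothetical. Recruitment may take place in hospital or by phone, and the documents do not say that cover is known then, so stratification has a practical cost in a trial of 60.

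**Conclusion.** The point holds as a loss of precision in the session comparison. Under the stated assumptions, cover explains about 18% to 39% of the variance in counts; at a 20% share, adjustment lowers the standard error by about a sixth (2.80 to 2.34). Everything rests on the assumed share, the 12-session cap and the assumed attendance. A smaller share or a milder cap would shrink the gain.

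Two further limits apply. It would be tempting to extend the finding to the primary outcome, since motivation is measured at completion or dropout and so possibly after shorter exposure in short-cover patients. The protocol says only that few covered sessions could potentially affect motivation, and nothing in it allows a size to be put on the RAI comparison. A stratification factor shown only in Figure 2 also cannot be ruled out, though the need to adjust the session comparison would remain.

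**What to change.** 1. Add the number of insurance-covered sessions to the characteristics collected, obtained at or before randomisation so that it is a baseline value, and report it by arm.
2. Replace the t-test on counts with a linear model (ANCOVA) of sessions on arm plus covered sessions, entered either as 36 versus fewer or as the number. Alternatively, analyse the percentage as the Measures section defines it. State in advance which is the main attendance analysis.
3. Optionally, add the same term to the RAI model, noting that its gain there is not quantified.

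The cost is one model degree of freedom and one extra baseline field, for a value the trial must obtain anyway. Stratifying the blocked randomisation by cover is optional: it would use one of the few factors practical with 60 patients and require cover to be known before allocation, while adjustment gives most of the precision gain.
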